### 6.5.2 Missing Outcome and Covariates

Subjects are included in the analyses to the extent of their available data; missing PK and efficacy data are not imputed. See Section 5.4.

Subjects with missing categorical data are counted in missing or unknown categories when appropriate. Subjects with missing numeric data are treated as missing completely at random when calculating summary statistics. For likelihood-based analyses (e.g., regression), missing at random is assumed.

Anti-SARS-CoV-2 Immunoglobulin Intravenous (Human) (NP-028), abbreviated as COVID-HIG  
EBS-CVH-006 Statistical Analysis Plan

### **6.5.3 Non-quantifiable Laboratory Data**

For laboratory data, unless otherwise specified in laboratory manuals or assay protocols, values below LLOQ are substituted with LLOQ/2 and values above the upper limit of quantitation (ULOQ) are substituted with ULOQ in the calculation of summary statistics. When values are reported as “>xx” or “<xx”, xx is considered as ULOQ or LLOQ, respectively. Original values as collected are provided in the listings.

### **6.5.4 Implausible Patient Reported Outcomes**

Not applicable.

## **6.6 Adjustment for Covariates**

No covariate adjustment, including adjustment for baseline SARS-CoV-2 antibody status, is performed since all analyses are descriptive in nature.

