2.1.1 Dose Rationale

The proposed dose for this clinical study (approximately 8–16 mg/kg based on an estimated participant weight of 50–100 kg) is within the dose levels tested in clinical studies of other licensed hyperimmune products and is expected to display similar safety and PK profile to those products. The selected dose for this clinical study is \approx 250,000 Alliance Units (AU), based on COVID-HIG product lot potency of 29,282 AU/mL in the wild-type neutralization assay (performed at the NIAID analytical laboratory), resulting in a dose volume of 8.5 mL. The COVID-HIG lot potency is derived using an internal standard that has been established in the NIAID sponsored treatment study INSIGHT-013 (clinical lot potency of COVID-HIG is 29,282 AU/mL). The selected dose is based on antibody titer data available from treatment studies with COVID-19 convalescent plasma (CCP) and SARS-CoV-2 antibody-based therapeutics and vaccine trials as well as emerging literature on protective antibody levels (17, 21, 22, 68, 69, 70). The proposed dose potency is within the range of COVID-HIG doses that have been used for treatment of hospitalized COVID-19 patients (INSIGHT-013; NCT04546581) and for early treatment of high-risk COVID-19 patients (INSIGHT-012; NCT04910269).

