4 SELECTION AND WITHDRAWAL OF SUBJECTS

4.1 Subject Inclusion Criteria

All participants must meet all the following inclusion criteria in order to be enrolled into the study:

1. Able and willing to provide written informed consent (voluntarily signed by the participant) prior to performing study procedures.
2. Females and males 18–59 years of age.
3. Have a BMI less than or equal to 35.0 kg/m².
4. Healthy, based on medical history (no chronic disease, no chronic therapy, no ongoing acute condition within four weeks prior to dosing), normal physical examination (no clinically significant findings in the opinion of the investigator), and screening laboratory assessments (no clinically significant findings in the opinion of the investigator).
5. No clinical symptoms suspicious for COVID-19 infection, as well as SARS-CoV-2 IgM antibody negative and no laboratory evidence of current SARS-CoV-2 infection (i.e., RT-PCR negative for SARS-CoV-2) at Screening.
6. Females must not be pregnant, or trying to become pregnant as demonstrated by either of the following A or B:
 - A. Not of childbearing potential: surgically sterile (at least six weeks post bilateral salpingectomy, bilateral oophorectomy, or hysterectomy); or post-menopausal (history of \geq 12 consecutive months without menses prior to randomization in the absence of other pathologic or physiologic causes and confirmed by follicle FSH level \geq 40 mIU/mL); OR
 - B. Women of childbearing potential who are not planning to be pregnant during the study period and who meet all of criteria i–iii:
 - i. Negative serum pregnancy test at the Screening Visit.
 - ii. Negative urine pregnancy test on Day 1 (a positive test will result in discontinuation from intervention).
 - iii. Using one of the following highly effective methods of contraception during the study:
 - Combined estrogen and progestogen, or progestogen-only hormonal contraception associated with inhibition of ovulation (e.g., implants, pills, patches) initiated \geq 30 days prior to Study Day 1.
 - Intrauterine device or hormone releasing IUS inserted \geq 30 days prior to Study Day 1.

Anti-SARS-CoV-2 Immunoglobulin Intravenous (Human) (NP-028), abbreviated as COVID-HIG
EBS-CVH-006, Version 3.0, 18 Feb 2022

7. Participant understands and agrees to comply with planned study procedures.

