### 2.2 Study Design and Conduct

This was a Phase 1, two-center, open-label, randomized study to evaluate one dose level of COVID-HIG administered IM, SC, or IV for safety and PK in healthy adults. Subjects that provided written informed consent and meet eligibility criteria were stratified based on their SARS-CoV-2 detectable antibody status ( $\geq$ lower limit of quantitation [LLOQ], but  $\leq$ 80 Alliance

Anti-SARS-CoV-2 Immunoglobulin Intravenous (Human) (NP-028), abbreviated as COVID-HIG  
EBS-CVH-006 Statistical Analysis Plan

units (AU)/mL on the Diasorin LIAISON SARS-CoV-2 S1/S2 IgG antibody assay) and undetectable antibody (<LLOQ) at screening and randomized in two cohorts. Cohort 1 consisted of 12 subjects; Cohort 2 comprised up to 24 subjects. Approximately thirty-six participants were to be enrolled and assigned equally to one of three study arms to receive a single IM, SC, or IV dose of COVID-HIG, respectively (Table 1). However, the study was truncated at 23 total randomized subjects in Protocol Amendment 3.0 due to the impact of high circulating SARS-CoV-2 omicron cases.

[figure not shown]
**Table 1** Study Design

Group	Study Arm	No. of Participants	Dosing Schedule – Day 1
Intramuscular	1	Up to 12	≈250,000 AU COVID-HIG IM 
Subcutaneous	2	Up to 12	≈250,000 AU COVID-HIG SC 
Intravenous	3	Up to 12	≈250,000 AU COVID-HIG IV 

Exact dose volume was determined based on the potency of the COVID-HIG clinical lot as defined in Alliance Units (AU) through the wild-type neutralization assay (Clinical lot potency: 29,282 AU/mL, 8.5 mL volume; target protein concentration: 100 mg/mL).

Enrollment into the study was staggered in Cohort 1, with no more than 5 participants dosed per day. Safety data were reviewed by a Safety Monitoring Committee (SMC; consisting of at least three independent external members) after all 12 participants in Cohort 1 completed at least 72 hours of safety follow-up. An overall decision by the SMC was made whether to proceed with full randomization (1:1:1) and dosing of the remaining study participants (Cohort 2, n=24).

**Figure 1** Schematic of Study Design and Visits

Anti-SARS-CoV-2 Immunoglobulin Intravenous (Human) (NP-028), abbreviated as COVID-HIG  
EBS-CVH-006 Statistical Analysis Plan

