### 8.2 Demographics and Baseline Characteristics

#### 8.2.1 Demographics

The following demographic characteristics are summarized as continuous variables using descriptive statistics (n, mean, SD, median, minimum, and maximum) by treatment arm for the Safety and PK populations:

- Age (years)
- Screening weight, height, BMI

The following demographic characteristics are summarized as categorical variables by treatment arm for the Safety and PK populations:

- Study site
- Age group (see definition in Section 6.3)
- Sex, and for women, childbearing potential
- Race
- Ethnicity

A subject listing of demographics is provided.

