#### 8.4.5 Pharmacokinetic Parameters

PK parameters in [Table 3](#) will be derived from the concentration-time data by non-compartmental analysis (NCA; i.e., log-linear trapezoidal) methods using actual sampling times; concentrations at nominal time points may be imputed using linear interpolation. If the actual sampling time is missing, but a valid concentration value has been measured, the nominal time as specified in the protocol may be used. Additional partial AUCs may be added as needed. For partial AUCs through a given time point, the partial AUC will be set to missing unless an actual time point occurs within  $\pm 10\%$  of the nominal timepoint for a given profile.

Bioavailability will be compared between administration routes, if data permit. An analysis of variance (ANOVA) model will be used with  $AUC_{0-inf}$  as the dependent variable and administration route as the fixed effect. The adjusted least square means will be used to estimate ratios of  $AUC_{0-inf\text{ IM}} / AUC_{0-inf\text{ IV}} * 100\%$ ,  $AUC_{0-inf\text{ SC}} / AUC_{0-inf\text{ IV}} * 100\%$ , and  $AUC_{0-inf\text{ IM}} / AUC_{0-inf\text{ SC}} * 100\%$  along with corresponding two-sided 90% CIs calculated based on the ANOVA. The width of the 90% CIs will be examined relative to the standard of [80%, 125%] for comparative bioavailability. If the area extrapolated from the time of the last measured concentration to infinity is greater than 40% of the total AUC for a subject profile, then the observation will be excluded from bioavailability analyses. No adjustment for multiplicity will be applied, and no formal hypothesis testing will be performed.

Anti-SARS-CoV-2 Immunoglobulin Intravenous (Human) (NP-028), abbreviated as COVID-HIG  
EBS-CVH-006 Statistical Analysis Plan

NCA PK parameter calculations and graphics are performed using SAS version 9.4 or higher.

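### Fixed dose, recorded weight, route-only model: a weight-adjusted AUC0-inf analysis beside the planned ANOVA is a cheap and probable, though not certain, gain in precision

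*SAP*

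**What the plan says.** - **Dose.** It is fixed in every arm. The footnote to SAP Table 1 (section 2.2) reads "Clinical lot potency: 29,282 AU/mL, 8.5 mL volume; target protein concentration: 100 mg/mL". Protocol 2.1.1 restates the dose per kilogram, "based on an estimated participant weight of 50–100 kg". The only limit on body size at entry is inclusion criterion 3 in Protocol 4.1: "Have a BMI less than or equal to 35.0 kg/m²".
- **Weight.** SAP 8.2.1 summarises "Screening weight, height, BMI" by arm for the Safety and PK populations. SAP 2.3.1 stratifies randomisation on screening antibody status alone.
- **Model.** SAP 8.4.5 fits an ANOVA with AUC0-inf "as the dependent variable and administration route as the fixed effect". It reports ratios with "corresponding two-sided 90% CIs calculated based on the ANOVA", and then: "The width of the 90% CIs will be examined relative to the standard of [80%, 125%] for comparative bioavailability". Protocol 9.4.2 and the synopsis specify the same model.
- **Covariates.** SAP 6.6 rules all of them out: "No covariate adjustment, including adjustment for baseline SARS-CoV-2 antibody status, is performed since all analyses are descriptive in nature".

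**The concern.** The reason given in SAP 6.6 does not settle the matter. A covariate can improve an estimate whether or not a hypothesis is tested, and these estimates carry CIs that are compared with a reference range. Comparing PK between routes makes up all of the secondary objectives (SAP 2.1.2).

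SAP Table 3 defines CL as dose divided by AUC0-inf. With the dose fixed, any dependence of clearance on weight therefore passes straight into AUC. With 7–8 per arm and no balancing on weight, some chance difference in mean weight between arms is to be expected. If weight matters, its effect sits in the residual variance and widens the CIs. With route as the only term, the adjusted least-squares means that SAP 8.4.5 promises are simply the arm means.

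**Working it through.** The documents give no AUC variability, no relation of AUC to weight and no expected CI width, so there is no design figure to reproduce apart from the dose: 8.5 × 29,282 = 248,897 AU, consistent with about 250,000.

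**Inputs from the documents.** N=23 with 7–8 per arm (SAP 4), taken as 8/8/7; two-sided 90% CI; weight range 50–100 kg. At about 850 mg (Protocol 5.1), that range gives 17 down to 8.5 mg/kg, a two-fold spread. Protocol 2.1.1 states about 8–16 mg/kg and Protocol 1.3.1 about 2–10 mg/kg; those passages must be reconciled, but the present point does not depend on it.

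**Assumptions.** AUC is analysed on the log scale. Between-subject CV is 20–50%. AUC varies as weight to the power −b, with b from 0.25 to 1. Reading 50–100 kg as ±2 SD, the SD of ln(weight) = ln(2)/4 = 0.173.

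**Step 1. Unadjusted CI, 8 v 7.** Log half-width = t(0.95, 20) × s × √(1/8 + 1/7), where s = √ln(1 + CV²). At CV 30%, s = 0.2936 and the half-width is 1.725 × 0.2936 × 0.5175 = 0.262. For a true ratio of 100%, the CI is 76.9–130.0%. At CV 20%, 40% and 50% it is 83.8–119.3%, 70.9–141.0% and 65.6–152.4%.

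**Step 2. Effect of adjustment.** Let R² be the share of within-arm variance of ln(AUC) explained by ln(weight). The adjusted half-width divided by the unadjusted one is [t(0.95, N−4)/t(0.95, N−3)] × √(1 + 1/(N−5)) × √(1 − R²). The middle factor is the expected cost of covariate imbalance. At N=23 this is (1.729/1.725) × √(1 + 1/18) × √(1 − R²) = 1.030 × √(1 − R²).

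| R² | Adjusted 90% CI, CV 30% | Change in half-width |
|---|---|---|
| 0 | 76.3–131.0% | +3.0% |
| 0.05 | 76.9–130.1% | +0.4% |
| 0.10 | 77.4–129.2% | −2.3% |
| 0.20 | 78.6–127.3% | −7.9% |
| 0.35 | 80.4–124.3% | −17.0% |

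Break-even is R² = 1 − 1/1.030² ≈ 0.06.

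**Step 3. What R² might be.** R² = b² × 0.173² / ln(1 + CV²).

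| CV | b=0.25 | b=0.5 | b=0.75 | b=1 |
|---|---|---|---|---|
| 20% | 0.05 | 0.19 | 0.43 | 0.77 |
| 30% | 0.02 | 0.09 | 0.20 | 0.35 |
| 40% | 0.01 | 0.05 | 0.11 | 0.20 |
| 50% | 0.01 | 0.03 | 0.08 | 0.13 |

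With b=0.5 and a CV of 40–50%, or with b=0.25 at any of these CVs, R² falls below break-even and the CI widens slightly.

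**Step 4. Chance imbalance.** The SD of the difference in mean ln(weight) between arms of 8 and 7 is 0.173 × 0.5175 = 0.090. A 1-SD imbalance moves the ratio by exp(0.090b) − 1: about 5% at b=0.5, 7% at b=0.75 and 9% at b=1.

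**Step 5. Simulation** (8/8/7, CV 30%, 20,000 trials per setting). The SD of the estimated log ratio goes from 0.153 to 0.140 at R² 0.20 and from 0.152 to 0.125 at R² 0.35. It rises from 0.152 to 0.156 at R² 0. The adjusted CI is the narrower one in 20%, 54%, 76% and 93% of trials at R² 0, 0.10, 0.20 and 0.35. Coverage is about 90% with or without adjustment.

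**Step 6. Smaller arms.** At five per arm, the ratio at R² = 0 is (1.796/1.782) × √(1 + 1/10) = 1.057, so the worst case is about 6% wider (5% by simulation) and break-even R² is about 0.10. At four per arm, break-even is about 0.15.

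**The case against.** The best case for the plan is that the comparison is made only if the data permit, without a hypothesis test, a sample size calculation or a pass/fail rule. Weight is tabulated by arm, so an imbalance will be visible. The unadjusted CI already carries the chance variation due to weight. The exclusions for pre-dose values above 5% of Cmax (SAP 8.4.2), extrapolated area above 40% (SAP 8.4.5) and COVID-19 (SAP 5.2) could shrink the set to a size where a covariate costs more. A weight term would also enter ahead of antibody status, the actual stratification factor. Finally, the protocol itself names route as the fixed effect, and the SAP reports enrolment as complete in an open-label study.

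Most of this stands as a limit on the claim. It argues for keeping the route-only model and for fixing any second model before AUC is examined by route. It does not rescue the reason in SAP 6.6, and a table of mean weights does not show how far an imbalance moved a ratio. Whether antibody status also belongs in the model is a separate question.

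A reader might infer more than the documents support:
- That weight is an established driver of exposure here. No section links weight to AUC; Protocol 2.1.1 uses weight only to express the dose per kilogram.
- That adjustment is bound to tighten the CIs. Steps 2 and 3 show that the direction depends on b and CV.
- That adjustment removes chance imbalance. It corrects only the part linear in ln(weight), with an estimated slope; imbalance in other factors stays.
- That randomisation failed to balance weight. No weight data are given; weight was simply not a stratification factor.

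**Conclusion.** The point holds as a cheap improvement in precision. The dose is fixed, weight is available, and being descriptive is not a sufficient reason to leave it out of estimates whose CIs are read against 80–125%.

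The plausible gain is a log half-width about 8% narrower (b=0.75) to 17% narrower (b=1) at CV 30%, with no gain below an R² of about 0.06. The downside is bounded at about 3% wider with all 23 in the model and 5–6% at five per arm. These sizes rest on the assumed CV, exponent and weight spread, and on the log scale. Omitting weight leaves the randomised comparison unbiased and its coverage at about 90%, so the planned analysis remains valid.

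**What to change.** In SAP 6.6 and 8.4.5, prespecify an ANCOVA of ln(AUC0-inf) on route and ln(screening weight). Report the three route ratios at the common mean weight, with two-sided 90% CIs, beside the protocol's route-only ANOVA. State that both models use log-transformed AUC0-inf: SAP 8.4.5 does not give the scale, and Protocol 9.2 says only that logs are used when appropriate. Replace the reason in SAP 6.6 accordingly, and show weight by arm for the participants who actually enter the model.

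The cost is one model term, one degree of freedom in the added model (20 to 19 with all 23 participants) and no new data. Reported as a second analysis, it leaves the protocol's model in place. If the ANCOVA is made the main model, Protocol 9.4.2 and the synopsis must be aligned with it. If AUC by route has already been seen, label the ANCOVA as added afterwards.

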## **6.7 Multicenter Study**

This study enrolled 23 subjects at two sites in the United States; data for subjects from both sites are pooled for all analyses. Data for subjects in Cohorts 1 and 2 are combined for all analyses.

## **6.8 Subgroup Analysis**

No formal subgroup analyses are planned for this Phase 1 study.

## **6.9 Multiplicity Adjustment**

Because all analyses are descriptive, multiplicity adjustment is not applicable in this study.

# **7 STUDY POPULATION CHARACTERISTICS**

## **7.1 Subject Disposition**

Subject disposition over the course of the study is summarized by treatment arm for all ITT population (randomized) subjects. Tabulations include the number of subjects randomized, treated, completed study medication treatment (see definition in Section 6.3), completed study, or withdrawn/terminated from the study. The reasons for study medication noncompletion and/or study withdrawal/termination are summarized. Reasons for screen failure are listed, if available.

## **7.2 Protocol Deviations**

Important PDs defined in Section 5.1 are summarized by category, subcategory, and treatment arm for all ITT population (randomized) subjects. All protocol deviations are listed by subject.

Anti-SARS-CoV-2 Immunoglobulin Intravenous (Human) (NP-028), abbreviated as COVID-HIG  
EBS-CVH-006 Statistical Analysis Plan

## 8 PHARMACOKINETICS ANALYSIS

### 8.1 Data Sets Analyzed

The number and percentage of participants in each analysis population is summarized by treatment arm and overall for all randomized subjects. Reasons for exclusion from analysis populations are summarized and listed by subject.

### 8.2 Demographics and Baseline Characteristics

#### 8.2.1 Demographics

The following demographic characteristics are summarized as continuous variables using descriptive statistics (n, mean, SD, median, minimum, and maximum) by treatment arm for the Safety and PK populations:

- Age (years)
- Screening weight, height, BMI

The following demographic characteristics are summarized as categorical variables by treatment arm for the Safety and PK populations:

- Study site
- Age group (see definition in Section 6.3)
- Sex, and for women, childbearing potential
- Race
- Ethnicity

A subject listing of demographics is provided.

#### 8.2.2 Medical History

Medical history is coded to system organ class (SOC) and preferred term (PT) according to the Medical Dictionary for Regulatory Activities (MedDRA). A summary table by treatment arm and a listing of medical history is provided for the Safety population.

#### 8.2.3 Prior and Concomitant Medications

Prior medications and concomitant medications are defined in Section 6.3. Prior and concomitant data are tabulated together by ATC classification, preferred drug name, and treatment arm for the Safety population. In the tabulation, ATC levels and standardized drug names within each ATC level are sorted in descending order of percentage in the Total column. A subject data listing of all medications is provided.

Anti-SARS-CoV-2 Immunoglobulin Intravenous (Human) (NP-028), abbreviated as COVID-HIG  
EBS-CVH-006 Statistical Analysis Plan

### **8.3 Treatment Compliance**

Treatment compliance is not applicable, as the study treatment is administered to the subjects in clinic.

### **8.4 Pharmacokinetic Analysis**

#### **8.4.1 Serum Concentration Data**

Serum concentration of SARS-CoV-2 binding antibody was measured by the anti-SARS-CoV-2 immunobinding IgG assay by Emergent laboratories. The assay has been validated for PK assessment, with an LLOQ value of 1 AU/mL and an ULOQ value of 48 AU/mL.

Subjects with incomplete data are evaluated on a case-by-case basis to determine if sufficient data are available for reliable estimation of PK parameters. A listing of PK sample collection times is provided, with flags to indicate sampling time deviations.

#### **8.4.2 Pre-dose Concentration Values and Endogenous Compounds**

The study drug SARS-CoV-2 binding IgG antibody is not expected to exist in the serum prior to receiving any dose, because a negative rapid SARS-CoV-2 IgG/IgM antibody and antigen test results were required for inclusion. A pre-dose serum sample for SARS-CoV-2 antibody was drawn on Day 1. Any anomalous concentration values observed prior to the first dose are identified and are set to 0 (zero) for the calculation of PK parameters. The original concentration values are used in statistical summaries. If the pre-dose value is greater than 5% of  $C_{max}$ , the affected PK profile is excluded from statistical summaries and analysis. Similarly, PK concentrations for the affected profile are excluded from statistical summaries. If necessary, background subtraction may be applied for PK analysis.

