9.4.2 Pharmacokinetic Analyses

Pharmacokinetic parameters will be estimated using standard non-compartmental methods (i.e., log-linear trapezoidal method). Subjects will be stratified based on their SARS-CoV-2 detectable antibody status ($>\text{LLOQ}$, but $\leq 80 \text{ AU/mL}$ on the Diasorin LIAISON SARS-CoV-2 S1/S2 IgG assay) and undetectable antibody ($\leq \text{LLOQ}$) at screening, with analyses done by antibody status (if possible) and overall per each arm. Actual times and not nominal times will be used in the analysis; concentrations at nominal time points may be imputed using linear interpolation. Participants with elevated baseline levels of SARS-CoV-2 antibodies or participants with inadequate number of PK time points (e.g., no pre-dose sample, or no measurable post-dose sample) may be excluded from the PK analysis. Outliers will be examined for possible exclusion from analysis, such as spiking antibody levels during the study attributed to active infection. Baseline subtraction may be employed, if necessary and where possible, using the mean of individual subject's pre-dose antibody titers. For partial AUCs through a given time point, the partial AUC will be set to missing unless an actual time point occurs within $\pm 10\%$ of the nominal timepoint for a given profile.

Bioavailability will be compared between administration routes, if data permit. An ANOVA model will be used with $\text{AUC}_{0-\text{inf}}$ as the dependent variable and administration route as the fixed effect. The adjusted least square means will be used to estimate ratios of $\text{AUC}_{0-\text{inf IM}} / \text{AUC}_{0-\text{inf IV}} * 100\%$, $\text{AUC}_{0-\text{inf SC}} / \text{AUC}_{0-\text{inf IV}} * 100\%$, and $\text{AUC}_{0-\text{inf IM}} / \text{AUC}_{0-\text{inf SC}} * 100\%$ along with

Anti-SARS-CoV-2 Immunoglobulin Intravenous (Human) (NP-028), abbreviated as COVID-HIG
EBS-CVH-006, Version 3.0, 18 Feb 2022

corresponding two-sided 90% CIs calculated based on the ANOVA. The width of the 90% CIs will be examined relative to the standard of [80%, 125%] for comparative bioavailability. If the area extrapolated from the time of the last measured concentration to infinity is greater than 40% of the total AUC for a subject profile, then the observation will be excluded from bioavailability analyses. No adjustment for multiplicity will be applied, and no formal hypothesis testing will be performed.

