Any anomalous concentration values observed prior to the first dose will be identified. Such values less than 5% of the observed C_{max} for the affected PK profile will be set to 0 (zero) for the calculation of PK parameters. The original concentration values will be used in statistical summaries. If the pre-dose value is greater than 5% of C_{max} , the affected PK profile will be excluded from statistical summaries and analysis. Similarly, PK concentrations for the affected profile will be excluded from statistical summaries.

Pharmacokinetic analyses will be performed separately for each administration route for the PK population, using the results of the binding IgG antibody assay (see Section 0). Comparative bioavailability will be presented between administration routes (IM to IV; SC to IV; and IM to SC), if data permit. Derived PK parameters, including both primary and secondary PK endpoints, will be tabulated by administration route for the PK population. Binding IgG SARS-CoV-2 antibody serum concentrations versus time curves will be summarized and plotted by administration route for the PK population.

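### SAP 8.4.2 wrongly says a negative rapid IgG test was required for entry, and neither document says whether the 5%-of-Cmax exclusion comes before or after baseline subtraction, so the planned antibody-positive stratum has no settled pre-dose rule

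*SAP*

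**What the plan says.** **Entry serology.** SAP 8.4.2 states that the antibody is not expected in pre-dose serum "because a negative rapid SARS-CoV-2 IgG/IgM antibody and antigen test results were required for inclusion". The protocol's screening steps (synopsis and 6.1) let a participant proceed on a negative rapid IgM and antigen result. Inclusion criterion 5 requires negative IgM and RT-PCR. Exclusion criterion 3 removes only participants with IgG above 80 AU/mL on the Diasorin assay. SAP 2.3.1 stratifies on detectable antibody and allowed 18 or 21 antibody-positive participants of 36.

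**Reporting.** Protocol 3.2.1.1 evaluates the primary PK endpoints in both strata. SAP 8.4.6 summarizes PK parameters by serostatus. Protocol 9.4.2 makes analysis by serostatus conditional on its being possible.

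**Pre-dose values.**
- Exclusion above 5% of Cmax: "the affected PK profile will be excluded from statistical summaries and analysis" (protocol 9.4.2) and "the affected PK profile is excluded from statistical summaries and analysis" (SAP 8.4.2).
- Optional exclusion, in the protocol only: "Participants with elevated baseline levels of SARS-CoV-2 antibodies or participants with inadequate number of PK time points" may be left out of the PK analysis.
- Optional subtraction: "Baseline subtraction may be employed, if necessary and where possible, using the mean of individual" pre-dose titers (protocol 9.4.2), and "If necessary, background subtraction may be applied for PK analysis" (SAP 8.4.2).
- Zero-setting: the protocol limits it ("Such values less than 5% of the observed" Cmax). In the SAP, anomalous pre-dose values "are identified and are set to 0 (zero) for the calculation of PK parameters" with no such limit.

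**The concern.** The SAP treats pre-dose IgG as an anomaly, while the design deliberately enrolls people who have it. Two consequences follow.

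First, the 5% exclusion taken at its word can delete profiles from a stratum that both documents intend to evaluate. Second, the same participant may be excluded (mandatory above 5%), excluded at discretion (protocol, for an undefined elevated baseline), or kept with baseline subtracted. Nothing fixes the order or the trigger. A participant above 5% before subtraction has a corrected pre-dose value of about zero afterwards, so the order alone decides whether the profile counts.

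In an open-label study with 7–8 participants per arm, that choice could be made after the profiles have been seen. It bears on AUC0-inf, which is a primary endpoint and the basis of the route ratios.

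**Working it through.** The plan gives no sample-size, power or expected-Cmax figure to reproduce. The check is therefore textual, followed by an illustration of size.

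**1. Entry rule against the SAP sentence**

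| Test | Protocol requirement | SAP 8.4.2 |
|---|---|---|
| IgM | negative | negative (agrees) |
| Antigen | negative | negative (agrees) |
| RT-PCR | negative | not mentioned |
| IgG | up to 80 Diasorin AU/mL eligible | negative (contradicts) |

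**2. The 5% test in PK-assay units.** SAP 8.4.1 gives LLOQ 1 and ULOQ 48 AU/mL. The smallest quantifiable pre-dose value passes only if Cmax ≥ 1/0.05 = 20 AU/mL. If Cmax were 48, the limit would be 0.05 × 48 = 2.4, so only pre-dose values of 1.0–2.4 would be both quantifiable and kept.

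**3. A kept, uncorrected profile.** Assume a flat baseline b at 5% of observed Cmax and a half-life of 24–30 days (the product-class range in protocol 2.1). Then b = 0.05/0.95 = 0.0526 of the drug peak. For an IV mono-exponential decline, drug AUC over 56 days per unit peak is (1 − e^(−56k))/k, with k = ln 2/half-life:
- 24 days: 27.75
- 30 days: 31.41
- Excess from baseline: 56 × 0.0526 = 2.95, or 10.6% and 9.4%.

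I repeated this at the protocol sampling times, with linear-up/log-down AUC and a best-fit terminal slope. IM/SC profiles used assumed bioavailability 0.6–0.8 and absorption rate 0.3–0.6 per day. Over all profiles, AUC0-last rises about 8–11%, AUC0-inf 13–17% and half-life 10–12%. At 1% of Cmax, AUC0-inf rises 2.4–3.1%.

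**4. Effect of zero-setting.** Zeroing the time-0 point removes the triangle before the 1-hour sample: ½ × 0.0526 × 1/24 = 0.0011. Against 27.75 + 2.95 = 30.70, that is 0.0036%. Endogenous IgG remains in every later sample.

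**5. Cost of losing the stratum (worst case).** The permitted share was 18/36 to 21/36 (50–58%). Applied to 23 randomized, 23 × 18/36 = 11.5 and 23 × 21/36 = 13.4 would be antibody-positive. About 10–12 profiles would remain, 3–4 per arm. For a true ratio of 100% on the log scale, the 90% half-width is t(0.95, N − 3) × √ln(1 + CV²) × √(1/n₁ + 1/n₂). At CV 30%:
- 8 vs 7, N = 23: 1.725 × 0.2936 × 0.5175 = 0.262, giving 77–130%.
- 4 vs 3, N = 11: 1.860 × 0.2936 × 0.7638 = 0.417, giving 66–152%.

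At CV 20% the interval goes from 84–119% to 75–132%. At CV 40% it goes from 71–141% to 58–173%.

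**6. Input to the subtraction.** Protocol 9.4.2 names the mean of the pre-dose titers, and a Day -1 PK sample is scheduled (protocol 6.3; Table 2 in both documents). Protocol 7.3 and SAP 5.4 omit Day -1. SAP 8.4.4 states both LLOQ/2 and zero for values below LLOQ when PK parameters are calculated. It also sets a missing pre-dose value to zero, whereas protocol 9.4.2 lets such a profile be excluded.

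**The case against.** The best defense is that the 5% paragraph in protocol 9.4.2 opens with anomalous values, so it may cover only those, leaving expected baseline IgG to the preceding paragraph on elevated baselines and subtraction. That reading is open. But anomalous is not defined, and SAP 8.4.2 closes it off by calling all pre-dose IgG unexpected.

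Several stronger readings are tempting and should not be drawn:
- **That every rule collides on one participant in both documents.** In the protocol, zero-setting below 5% and exclusion above 5% are complementary. The elevated-baseline exclusion is in the protocol only; SAP 8.4.3 is a general outlier provision. The SAP's loss of the 5% limit on zero-setting is a discrepancy, but numerically almost nothing.
- **That the stratum will certainly be lost.** Setting Diasorin values of 15–80 AU/mL against 5% of Cmax suggests so, but no conversion between Diasorin, neutralization and PK-assay units is given, nor any expected Cmax or stratum count.
- **That SAP 5.5 contradicts the protocol's subtraction input.** It is a general baseline definition; only the protocol names an input for subtraction.
- **That subtraction is statistically superior to exclusion.** That would depend on the drug peak, how fast endogenous IgG wanes and which arm has seven participants. None of these is given.

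It also stands that the analyses are descriptive and exclusions must be listed with reasons (SAP 6.4, 8.4.3, 8.4.6). The choice would be visible, but disclosure is not prespecification.

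**Conclusion.** The point holds and should be fixed. The IgG statement in SAP 8.4.2 contradicts the eligibility criteria and the SAP's own randomization section. The exclusion that follows it can, read literally, remove participants the plan intends to report. It also conflicts with the protocol's discretionary exclusion and with the optional subtraction in both documents, with no stated order.

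The rule chosen matters: AUC0-inf is about 13–17% too high if a baseline at 5% of Cmax is left in, or the 90% CI widens from 77–130% to 66–152% if the whole stratum is dropped. The first figure assumes a flat baseline and a 24–30 day half-life. The second assumes CV 30%, the planned serostatus mix carried over to the 23 randomized, and every antibody-positive profile failing the test. The textual finding needs none of these assumptions. The number of profiles affected cannot be determined from the documents.

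**What to change.** 1. In SAP 8.4.2, replace the sentence: entry required negative IgM, antigen and RT-PCR; endogenous IgG is expected in the antibody-positive stratum and is not anomalous.
2. State that neither the 5% rule nor the elevated-baseline provision by itself removes antibody-positive profiles. For any participant with quantifiable PK-assay pre-dose IgG, whatever the Diasorin stratum, subtract the mean of the Day -1 and Day 1 pre-dose values before deriving parameters. Run the 5% exclusion as a sensitivity analysis. Say what happens when the mean is below LLOQ (for example 1.0 and an imputed 0.5 average 0.75) and when both pre-dose samples are missing.
3. Report seronegative-only parameters and route ratios beside the baseline-corrected overall results. List each pre-dose value as a percentage of Cmax.
4. Add the Day -1 sample to SAP 5.4 and protocol 7.3, and keep one below-LLOQ pre-dose rule in SAP 8.4.4.

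**Cost.** SAP wording and one derivation; no new samples. Changing the protocol generally needs a formal amendment with IRB approval (protocol 13.2). Otherwise the SAP should state the departure.

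**Downside.** Constant subtraction biases AUC downward if endogenous IgG wanes. With an assumed waning half-life of 60–180 days and drug half-life of 27 days, a baseline near 5% of the IV drug peak lowers AUC0-inf by about 2–6% (IV) and 3–11% (IM/SC). At a quarter of that peak the loss is 11–25% and 15–40%. That is why the seronegative-only results must stand beside the corrected ones.
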